## APPENDIX 2. INCIDENCE OF FALLS DIARY

MARIN Protocol 0171 - Fall Diary

Subject ID: \_\_\_\_\_

Visit Dispensed: \_\_\_\_\_

Date Returned: \_\_\_\_\_

**Instructions:**

- 1) For each Time of Day, entry should be made at the end of that time period.
- 2) If you did not fall or have a near-fall, put a check mark in the No Falls or No Near-Falls box for that time of day.
- 3) If you had a fall or near-fall, record the number of Falls or Near-Falls in the appropriate box for that time of day.

**Definitions:**

A fall is defined as: an unexpected event in which you come to rest on the ground, floor, or lower level.

A near-fall is defined as: losing your balance but managing to stay upright, for example by holding on to something or someone.

Day of the Week/ Date	Time of Day	No Falls	No Near-Falls	Falls	Near-Falls
Day of the Week:	Morning: Awakening to 12PM			Number =	Number =
	Afternoon: 12 PM to Bedtime			Number =	Number =
	Night: Bedtime to Awakening			Number =	Number =
Date:	Morning: Awakening to 12PM			Number =	Number =
	Afternoon: 12 PM to Bedtime			Number =	Number =
	Night: Bedtime to Awakening			Number =	Number =
Day of the Week:	Morning: Awakening to 12PM			Number =	Number =
	Afternoon: 12 PM to Bedtime			Number =	Number =
	Night: Bedtime to Awakening			Number =	Number =
Date:	Morning: Awakening to 12PM			Number =	Number =
	Afternoon: 12 PM to Bedtime			Number =	Number =
	Night: Bedtime to Awakening			Number =	Number =
Day of the Week:	Morning: Awakening to 12PM			Number =	Number =
	Afternoon: 12 PM to Bedtime			Number =	Number =
	Night: Bedtime to Awakening			Number =	Number =
Date:	Morning: Awakening to 12PM			Number =	Number =
	Afternoon: 12 PM to Bedtime			Number =	Number =
	Night: Bedtime to Awakening			Number =	Number =
Day of the Week:	Morning: Awakening to 12PM			Number =	Number =
	Afternoon: 12 PM to Bedtime			Number =	Number =
	Night: Bedtime to Awakening			Number =	Number =
Date:	Morning: Awakening to 12PM			Number =	Number =
	Afternoon: 12 PM to Bedtime			Number =	Number =
	Night: Bedtime to Awakening			Number =	Number =

If you recorded a Fall or Near Fall above, were you injured as a result? Please check one: No  or Yes

If you checked "Yes", please remember to discuss the injury with the site staff at your next visit.

TO BE COMPLETED BY SITE PERSONNEL ONLY: I confirm that I have carefully reviewed all entries in this diary.

Signature of Reviewer: \_\_\_\_\_ Date of Review: \_\_\_\_\_  
 Reviewer Print Name: \_\_\_\_\_ Reviewer Title: \_\_\_\_\_

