### SCHEDULE OF STUDY PROCEDURES

**Table 1: Schedule of Study Procedures (Visits 1 – 6)**

Each study visit for each subject may be conducted either in clinic or remotely									
Study Week (Visit/Telephone):	Week 0 Visit 1 (0170 Visit 9)	Week 2 Visit 2 +/- 3 days	Week 6 Visit 3 +/- 3 days	Week 10 Visit 4 +/- 7 days	Week 14 Telephone 1 +/- 3 days	Week 18 Visit 5 +/- 7 days	Week 22 Telephone 2 +/- 3 days	Week 26 Visit 6 +/- 7 days	Early Termination up to Week 26
Informed Consent	X								
Inclusion / exclusion criteria	X								
Medical history, including smoking history	X								
Concomitant Medications	X a	X	X	X	X	X	X	X	X
C-SSRS	X a	X	X	X		X		X	X
[REDACTED]	[REDACTED]	[REDACTED]	[REDACTED]	[REDACTED]		[REDACTED]		[REDACTED]	[REDACTED]
Vital signs (heart rate, blood pressure, respiratory rate and body temperature)	X a, b	X b	X b	X b		X b		X b	X b
Physical examination	X a			X				X	X
Neurological examination	X a			X				X	X
12-lead electrocardiogram e	X a			X				X	X
Pregnancy Test	X a, c			X c				X c	X c
Safety Labs (chemistry, hematology, urinalysis)	X a			X				X	X
Dosing, Incidence of Falls, and Midodrine Diaries	X a	X	X	X		X		X	X
Adverse Events	X a	X	X	X	X	X	X	X	X
Dispense Study Drug	X d	X d	X d	X d		X d		X d	
Study Drug Dosing	X d								
Collect Study Drug		X	X	X		X		X	X

a. Study 0170 procedures conducted at Visit 9 will serve as the baseline assessment for Visit 1 of Study 0171.  
 b. Vital signs will be assessed after the subject has been resting for at least 5 minutes in the seated or supine position.

- c. In women of childbearing potential only, urine beta human chorionic gonadotropin ( $\beta$ hCG) test will be performed and if positive, confirmation with serum  $\beta$ hCG test is required. The pregnancy test must be confirmed negative for a subject to be eligible for this study.
- d. Study drug will be ingested in the morning at approximately the same time of day with 8 ounces of water. The exact time and day of dosing will be recorded on the mornings of study visits. Subjects must be reminded to maintain an adequate fluid intake during their scheduled visits. Subjects will start taking study drug on the day after Visit 1.

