#### **6.4.3.8. Incidence of Falls Diary**

Falls in subjects with symptomatic nOH are common and potentially catastrophic. They can lead to serious injuries including hip fractures or head trauma; furthermore, fear of falling can limit mobility and physical activity. Thus, incidence of patient-reported falls is being captured in a diary. Assessments will be performed as specified in the Schedule of Study Procedures ([Table 1](#)). An example of the diary is provided in [Appendix 2](#).

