### 7.4.3. Serious Adverse Event and Adverse Event of Special Interest Reporting Timeline

All SAEs and AESIs must be reported to Clinical Safety and Pharmacovigilance within 24-hours of the time the Investigator or his/her designee becomes aware that an SAE or AESI has occurred, whether or not the event is considered to be related to study drug. If the initial SAE or AESI is reported by telephone, a written report signed by the Investigator must be submitted within 24-hours.

The SAE/AESI Report Form must be completed in accordance with the SAE/AESI Report Form Completion Guidelines. If all information on the SAE/AESI Report Form is not available at the time of the initial report, follow-up SAE or AESI reports will be completed and submitted.

To report an SAE or AESI, complete and send the SAE/AESI Report Form to the following:

Theravance Biopharma Clinical Safety

[REDACTED]

For medical questions regarding an SAE or AESI, contact the medical monitor by telephone as follows:

Medical Monitor Contact Information:

[REDACTED]

[REDACTED]

[REDACTED]

For fatal or life-threatening events, also fax copies of hospital case reports, autopsy reports, and other documents when requested. Additional information may be requested from the Investigator to ensure the timely completion of accurate safety reports.

An SAE may qualify for reporting to regulatory authorities if the SAE is possibly attributable to the study drug and is unexpected/unlisted based on the current TD-9855 IB. In this case, all Investigators will receive notification of the event. The Investigator is responsible for notifying the Institutional Review Board or Ethics Committee and documenting the notification, as required by local regulatory authorities and in accordance with the local institutional policy.

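### The sample falls diary points an injured subject to the next visit and never asks for prompt contact, so a serious injury that is not volunteered could reach the site up to 38 days later

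*Protocol*

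**What the plan says.** The form in Protocol Appendix 2 closes with a yes/no item on whether any recorded fall or near-fall caused an injury. A subject who answers yes reads: "please remember to discuss the injury with the site staff at your next visit". That is the form's only instruction on what to do after an injury. Its numbered instructions deal solely with when and how to fill in the boxes.

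Protocol Section 6.4.3.8, which introduces the diary, states: "Falls in subjects with symptomatic nOH are common and potentially catastrophic". It names hip fracture and head trauma among the possible injuries, and it describes Appendix 2 as an example of the diary.

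Protocol Section 7.4.3 requires SAEs and adverse events of special interest (AESIs) to be reported "within 24-hours of the time the Investigator or his/her designee becomes aware that an SAE or AESI has occurred". The clock runs from awareness, not from the event.

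Protocol Table 1 has a row for "Dosing, Incidence of Falls, and Midodrine Diaries". It is marked at Weeks 0, 2, 6, 10, 18 and 26 and at early termination up to Week 26. The Week 14 and Week 22 contacts are labelled as telephone contacts, not visits, and carry no diary mark. Sections 6.3.6 and 6.3.8 give their content as a review of concomitant medications and an assessment of AEs, SAEs and AESIs. Table 2, for the period after Week 26, schedules no diary.

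**The concern.** Long-term safety is the primary objective, and incidence of falls is listed among the primary safety endpoints. An injury that leads to inpatient admission is an SAE under Protocol Section 7.1.2. For such an injury, the form the subject has in hand ought to shorten the time until the site hears of it. Instead it names the next visit, treats a bruise and a fracture alike, and is silent on earlier contact.

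Two things depend on the site knowing: the 24-hour report to the sponsor, and the investigator's judgement, listed among the stopping rules in Section 3.1, on whether further dosing poses a safety concern. If a subject does just what the form says, both start later than they need to. The question is how much later.

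**Working it through.** The documents give no figure for this delay, so there is none to reproduce. The check is date arithmetic on Protocol Table 1.

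**Inputs.** Visit 1 is Day 0. Visits 2 and 3 are at Weeks 2 and 6, each ±3 days. The later entries read "Week 10 Visit 4 +/- 7 days", "Week 18 Visit 5 +/- 7 days", "Week 26 Visit 6 +/- 7 days" and "Week 14 Telephone 1 +/- 3 days". Telephone 2 is at Week 22, also ±3 days.

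**Formulas.** Nominal gap = (later week − earlier week) × 7 days. Longest gap = nominal gap + window of the earlier contact + window of the later contact.

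**Gaps between diary-review visits**

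| Interval | Nominal (days) | Longest (days) |
|---|---|---|
| Visit 1 to 2 | 14 | 14 + 0 + 3 = 17 |
| Visit 2 to 3 | 28 | 28 + 3 + 3 = 34 |
| Visit 3 to 4 | 28 | 28 + 3 + 7 = 38 |
| Visit 4 to 5 | 56 | 56 + 7 + 7 = 70 |
| Visit 5 to 6 | 56 | 56 + 7 + 7 = 70 |

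In study days, Visit 4 at its earliest is Day 63 and Visit 5 at its latest is Day 133, which gives 70. Visit 5 at its earliest is Day 119 and Visit 6 at its latest is Day 189, again 70. So the two longest visit intervals are 8 weeks nominally and 70/7 = 10 weeks at most.

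**Gaps between scheduled adverse event enquiries, with the two calls added**

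| Interval | Nominal (days) | Longest (days) |
|---|---|---|
| Visit 4 to Telephone 1 | 28 | 28 + 7 + 3 = 38 |
| Telephone 1 to Visit 5 | 28 | 28 + 3 + 7 = 38 |
| Visit 5 to Telephone 2 | 28 | 28 + 7 + 3 = 38 |
| Telephone 2 to Visit 6 | 28 | 28 + 3 + 7 = 38 |

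The calls bring the longest gap down from 70 to 38 days, or 38/7 = 5.4 weeks. They cannot bring it lower, because Visit 3 to Visit 4 has no call between and can itself reach 38 days (Day 39 to Day 77).

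**Typical rather than worst case.** If injuries fall evenly across an interval (an assumption), the mean wait is half of it. That is 28/2 = 14 days to the next adverse event enquiry across a nominal 4-week gap, and 56/2 = 28 days to the next visit across a nominal 8-week gap.

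**The case against.** The best defence is that the diary is not the SAE reporting route. It supports a descriptive falls summary (Protocol Section 8.5.7, SAP Section 8.7). Protocol Section 6.4.3.2 allows spontaneous reports from the subject or caregiver. Section 6.4.3.9.4 allows unscheduled visits, in clinic or remote, without sponsor approval. The calls already ask about adverse events, and an injury from a fall is one. The form is only an example, and consent-form or manual text that may ask for prompt contact is not available here. All of this is correct and it limits the point. It does not remove it: a spontaneous report requires the subject to do something this form does not ask for, and an unscheduled visit for an injury normally follows once the site has heard of it.

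A reader might go further in five ways that the documents do not support.

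- **That the subject is told to wait.** The sentence is a reminder. Nothing in it forbids or discourages earlier contact.
- **That the site may hear nothing for 8 to 10 weeks.** That is the interval between visits. It becomes the delay only if the subject is asked about adverse events on the call and still leaves the injury out.
- **That late reports push onset dates into the partial-date rules of SAP Section 10.2.2.** The diary has date fields and time-of-day rows, to be completed as each period ends, and those rules apply to missing or incomplete dates, not late ones. The injury item has no date of its own and is not tied to a particular fall, but that is a separate and smaller gap.
- **That review by the independent data monitoring committee is delayed.** Section 8.7 is redacted, and the visible text says only that review is periodic.
- **That the 12-week contact intervals after Week 26 make it worse.** No diary is scheduled then, so this instruction does not apply.

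**Conclusion.** The point holds as a gap in the wording of a safety-reporting form, limited to the first 26 weeks. The sample diary links injury reporting to the next visit and asks for no prompt contact, which fits poorly with the weight Section 6.4.3.8 gives to falls and with a reporting clock that depends on site awareness.

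A serious fall injury not volunteered by the subject or caregiver could stay unknown to the site for up to 38 days (about 5.4 weeks). It could stay unknown for up to 70 days if the subject follows the form literally and does not raise it on the call. Both are upper limits: they assume an injury just after one contact and both windows used in full. They also assume that the fielded diary matches Appendix 2 and that no other subject-facing text asks for earlier contact, neither of which can be checked here.

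No statistical figure or planned analysis changes. The SAP records that the sponsor stopped the study early with 110 subjects enrolled, so the practical value lies in correcting the plan as written and in any further use of the form.

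**What to change.** Reword the closing sentence of Appendix 2 to say, in substance: *If you checked Yes, please contact the site staff as soon as possible about the injury, and discuss it again at your next visit.* Check it against the consent form and the study manual so that all subject-facing text gives the same message.

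Optionally, add a specific prompt about injury from a fall to the adverse event assessment at the Week 14 and Week 22 calls. The general enquiry already covers such injuries, so this is a memory aid and not a new assessment.

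The cost is one sentence on a form and, if adopted, one line in two existing call scripts. The downside is a few more calls to sites about minor injuries. Visit timing, treatment and analysis stay as they are.

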### APPENDIX 3. DOSING DIARY

#### Marin 0171 Dosing Diary

Subject ID: \_\_\_\_\_

Date Diary Dispensed: \_\_\_\_\_ Date Diary Returned: \_\_\_\_\_

**Instructions:** YOU MUST BRING THIS DIARY AND YOUR STUDY MEDICATIONS TO EVERY STUDY VISIT

- 1) Please indicate the day of the week, date, time, and any comments.
- 2) Each "Time" entry should be immediately after taking the medication.
- 3) Dosing should occur every day at approximately the same time and AM or PM should be circled
- 4) Do not use any recreational drugs or drink excessive alcohol during the study period.
- 5) Do not participate in another investigational study.
- 6) Refrain from making any significant dietary changes throughout the duration of the study.
- 7) Ensure adequate fluid intake during the scheduled visits.
- 8) Subjects who are smokers will be recommended to either stop smoking >7 days before first dose or maintain a constant smoking habit during the entire course of the study.

Day of the Week/ Date	Time	Comments (E.g.: -Reason for missed or partial dose -Significant Dietary Changes)
Day of the Week:  Date:	_____:____ AM / PM	
Day of the Week:  Date:	_____:____ AM / PM	
Day of the Week:  Date:	_____:____ AM / PM	
Day of the Week:  Date:	_____:____ AM / PM	
Day of the Week:  Date:	_____:____ AM / PM	
Day of the Week:  Date:	_____:____ AM / PM	
Day of the Week:  Date:	_____:____ AM / PM	
Day of the Week:  Date:	_____:____ AM / PM	

TO BE COMPLETED BY SITE PERSONNEL ONLY:	
I confirm that I have carefully reviewed all entries in this diary.	
Signature of Reviewer: _____	Date of Review: _____
Reviewer Print Name: _____	Reviewer Title: _____

[REDACTED]

[REDACTED]

**APPENDIX 5.** [REDACTED]

[REDACTED]

- | [REDACTED]
- | [REDACTED]
- | [REDACTED]
- | [REDACTED]
- | [REDACTED]

## APPENDIX 6. OVERVIEW OF DECENTRALIZATION PLAN

This appendix provides information for those sites who choose to conduct remote study visits for at least one of their subjects. Detailed instructions for the conduct of both in clinic and remote study visits can be found in the Study Procedures Manual, which must be used in conjunction with the protocol.

The Principal Investigator retains accountability for all data collected and processed for each study subject either via in clinic or remote visits. Procedures to protect subject safety, subject privacy, and data integrity will be followed by all personnel (clinic and home health personnel) involved in study conduct.

### Rationale for Decentralized Platform:

Considering the frailty of the symptomatic nOH subject population, the risk of future exposure to COVID-19 via in clinic visits, the unpredictable duration of the pandemic, and the potential for additional waves of the COVID-19 pandemic, the study will utilize an operational design featuring the ability for sites to conduct protocol required visits as either in clinic or remote visits.

[figure not shown]
### Selection of Visit Modality:

Given the challenges presented by the COVID-19 pandemic the trial utilizes an operational design featuring the ability to conduct protocol required visits as either in clinic or remote visits. Based upon discussion with the subject, the Investigator may conduct each study visit for a given subject either in clinic or remotely. The Investigator is recommended to conduct in clinic study visits consistent either with the standard of care for a subject outside of a clinical trial or at a minimum once per year for each subject.

Tools and systems are available to sites and subjects to support remote visits (e.g., direct to subject shipping of study medication and other study supplies, standardized HIPAA/GDPR compliant telemedicine platform, in-home health nurses).

For those sites who opt to use remote visits (the decentralized platform) for study conduct, all required regulatory and ethics committee or IRB approvals will be obtained before utilization of remote study visits under the decentralized platform.

Sites will use the most recent approved version of the Informed Consent Form to obtain subject consent for remote study visits.

### Conduct of the Study and the Decentralized Platform:

All sites will follow the protocol Schedule of Procedures (see [Table 1](#) and [Table 2](#) of the protocol) for study visit scheduling and protocol required procedures (either in clinic or remote). Refer to the Study Procedures Manual for detailed instructions for conducting subject assessments in clinic and remotely. These instructions have been provided to ensure the method and conduct of each assessment is consistent across sites and subjects for both in clinic and remote visits.

Training and mechanisms will be available to sites and subjects to support remote visits.

Sites will continue to follow their established processes and procedures for the conduct of in-clinic study visits.

**Study operations support for remote visits:**

Tools and systems are provided by the Sponsor and are available to sites and subjects to support remote visits:

- A. A courier service has been engaged to ship investigational study drug and other study supplies to the subject (or designee).
- B. A standardized HIPAA/GDPR compliant telemedicine platform will be provided so that site personnel can participate in remote visits that are conducted in the subject's home (or designated location), utilizing Home Health Providers.
- C. A Home Health Provider (HHP) service has been employed.
- D. Medically qualified and trained HHP staff employed will visit the subject's home (or designated location) and will work with Site Staff (SS) to conduct each remote study visit from the privacy of the subject's home or designated location (such as a caregiver's home).
- E. During these remote visits, in coordination with Site Staff, the HHPs will use the Rater Station to facilitate collection of patient reported outcomes, will collect blood samples for safety labs and PK testing, will collect ECGs, and will measure the subject's vital signs.
- F. All data collected during the remote visits will be transferred to the Investigator and the study site via established processes (either electronically or on paper).

Data signifying where the visit was conducted (in clinic or remote), how the data were collected, and who collected data remotely will be recorded in subject source documents and in the clinical study database.

A Home Health Provider Delegation Log will be used to record the names of HHP professionals who assist Site Staff with the conduct of the remote visits. This separate delegation log will distinguish between those individuals who are part of the site staff (recorded on Site Delegation Log) and those who are employed by the HH Provider.

**Logistics Arrangements for Remote Visits:**

For remote study visits, the home health personnel conducting the visit will be notified by the clinic-based study staff of each upcoming scheduled visit for the study subject(s). The clinic-based staff will coordinate with the home health personnel to ensure access to all necessary subject source documents, required equipment, and procedural instructions to complete the remote assessment.

Clinic-based staff will participate in the remote study visit(s) via the established telemedicine platform available for the study.

Home health personnel will transfer the source documents completed during the remote visit to the Investigator's site via established processes. Home health personnel will transfer via established secure means the data collected in electronic format to the appropriate data repository for inclusion in the clinical database.

Data collected in paper format (subject diaries and any handwritten source notes) will be retrieved by HHP during the remote visit and will be returned to the Investigator's site.

Appropriate technical support and training will be provided to facilitate remote conduct of required study assessments.

Laboratory samples collected by home health personnel during the remote visit will be prepared for shipment to designated laboratories following established collection and shipping procedures.

**Summary:**

In closing, the tools, mechanisms, and processes put into place as part of the Decentralized Platform support sites and subjects who choose remote visits. Further, they protect subject safety, privacy, and consistency in data collection and reporting. In the event of future resurgences of the COVID-19 pandemic, these tools, mechanisms, and processes will be available to sites and subjects who have selected the in clinic visit modality.

## 1. LIST OF ABBREVIATIONS

**Table 1: List of Abbreviations**

Abbreviation	term
AE	adverse event
ATC	Anatomic Therapeutic Chemical
BP	blood pressure
BMI	body mass index
CRF	case report form
C-SSRS	Columbia-Suicide Severity Rating Scale
DBP	diastolic blood pressure
HR	heart rate
MedDRA	Medical Dictionary for Regulatory Activities
SD	standard deviation
SAE	serious adverse event
SAP	statistical analysis plan
SBP	systolic blood pressure
VAS	visual analogue scale
WHODD	World Health Organization Drug Dictionary

